5.4.2 Kaplan-Meier estimates

To analyze time to event variables (DOR and PFS) an estimate of the survival function will be constructed using **Kaplan-Meier (product-limit) method** as implemented in PROC LIFETEST with METHOD=KM option (see example below). The median time to event and estimated event rates at different time points will be estimated, along with associated 95% two-sided CIs derived based on the complementary log-log transformation. This will be conducted via the SAS procedure LIFETEST. The TIME statement will include a variable with survival times (*survtime* in the example below) and a (right) censoring variable (*censor* in the example below) with a value of 1, representing censoring:

```
PROC LIFETEST data = dataset
```

```
    METHOD = KM
```

```
    CONFTYPE=LOGLOG;
```

```
TIME survtime*censor(1);
```

```
RUN;
```

```
/* survtime represents variable containing event/censor times;
```

```
censor represents censoring variable (1 = censored, 0 = event); */
```

Kaplan-Meier survival and failure function estimates from this procedure will be used to construct the Kaplan-Meier figures

Median survival will be obtained along with 2-sided 95% CIs calculated from PROC LIFETEST output using the method of [Brookmeyer & Crowley, 1982](#).

Kaplan-Meier estimates with 2-sided 95% CIs at specific time points will be summarized. The time points can be expressed in weeks or in months depending on the time-to-event variable. The CIs will be constructed using Greenwood's formula [[Collet, 1994, p.23](#)] for the standard error of the Kaplan-Meier estimate.

The Kaplan-Meier graphs will be constructed using SAS software.

5.4.3 Confidence interval for response rate

ORR will be summarized in terms of percentage rates with 95% CIs. An exact binomial confidence interval (implemented using SAS procedure FREQ with EXACT statement for one-way tables) will be calculated ([Clopper & Pearson, 1934](#)).

SAS procedure FREQ will be used to estimate the proportion of responders (binary outcome = 1 or "Yes"), along with the associated 95% ($=100 \times (1 - \text{two-sided alpha level})$) two-sided Pearson-Clopper CI for the hypothesis test of the *null proportion* (0.25). These estimates are obtained as follows:

```
proc freq data = dataset;  
  table binary event /  
    binomial (  
      level = "Yes")  
      alpha = two-sided alpha level;  
  exact binomial;
```

When there are no responders, SAS does not produce a CI by default. To obtain a CI in this situation, PROC FREQ is used as specified above except changing `level="No"`. From the results of this modified procedure, the values in percent of the LCL and UCL of a 0% response rate are calculated as follows:

$$LCL_{\text{LEVEL}=\text{"Yes"}} (\%) = 100\% - UCL_{\text{LEVEL}=\text{"No"}} (\%)$$

$$UCL_{\text{LEVEL}=\text{"Yes"}} (\%) = 100\% - LCL_{\text{LEVEL}=\text{"No"}} (\%)$$

5.5 Safety evaluations

The text below gives more detailed instructions and rules needed for programming of the analyses described in [Section 2.8](#)

5.5.1 Multiple assessments within post-baseline visits

For all analyses regarding abnormal assessments or analyses based on worst or best post-baseline value (laboratory, ECGs, vital signs, ECOG performance status), all post-baseline values will be included (scheduled, unscheduled, repeat). All unscheduled and repeat measurements will be included in listings.

Laboratory Data

For laboratory data, assessments can be collected from both local and central laboratory on the same date. For shift tables using CTC grades to compare baseline to the worst post-baseline value, the assessment with worst post-baseline value is used for analyses irrespective of the source. For LFT summaries, where concurrent measurements are used in the calculation of number and percentage of patients with worst post-baseline values, the assessment with worst post-baseline value is used (since worst values are based on the largest ratio of lab value to its ULN for each patient) although the worst values for the different parameters may be coming from different laboratories.

ECGs

For all patients, three ECGs are targeted to be measured at the protocol-defined (nominal) time-points. If a patient has more than one measurement at a nominal time point, the average of all available measurements associated with the nominal time point will be used for the analyses.

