#### 7.2.2.5.4 Electrocardiogram (ECG)

A standard 12-lead ECG will be performed in accordance with [Table 7-4](#).

Interpretation of the tracing will be made by a central ECG lab. Each ECG tracing should be labeled with the study number, patient initials, patient number, date, and kept in the source documents at the study site. Only clinically significant abnormalities will be recorded in the AE eCRF page. Clinically significant abnormalities at screening/baseline should be recorded on the Relevant Medical History/Current Medical Conditions eCRF page. Clinically significant findings must be discussed with the Novartis Medical Monitor prior to enrolling the patient in the study. In the case of QTc >500 ms an ECG should be repeated daily until the QTc prolongation has resolved to grade 1 or less.

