**Table 7-4 Central ECG collection plan**

| Cycle                          | Day              | Time   | ECG Type       |
|--------------------------------|------------------|--|----------------|
| Screening/
Baseline | -28 to -1 | Anytime   | 12 Lead |
| 1                              | 1                | Post-dose 4 hours (ECG should be performed just prior to drawing PK sample if both are scheduled simultaneously) | 12 Lead        |
| 1                              | 1                | Post-dose 6 hours (ECG should be performed just prior to drawing PK sample if both are scheduled simultaneously) | 12 Lead        |
| 2                              | 1                | Post-dose 4 hours (ECG should be performed just prior to drawing PK sample if both are scheduled simultaneously) | 12 Lead        |
| 2                              | 1                | Post-dose 6 hours (ECG should be performed just prior to drawing PK sample if both are scheduled simultaneously) | 12 Lead        |
| 3                              | 1                | Pre-dose (ECG should be performed just prior to drawing PK sample if both are scheduled simultaneously)          | 12 Lead        |
| 4                              | 1                | Pre-dose (ECG should be performed just prior to drawing PK sample if both are scheduled simultaneously)          | 12 Lead        |
| 5-16                           | 1                | Pre-dose   | 12 Lead        |
| Even #
cycles ≥18           | 1                | Pre-dose   | 12 Lead        |
| EOT                            | 1                | Within 14 days (up to 21 days) of last dose  | 12 Lead        |

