- For each of the ECG parameters (HR, and QTc, QT, QRS and PR intervals) descriptive statistics at baseline, at each post-baseline time point and changes from baseline at each post-baseline time point
- For each of the QTc and QT intervals, shift tables based on notable parameter categories (≤ 450 , $>450 - \leq 480$, $>480 - \leq 500$, >500 ms) at baseline and the worst post-baseline value observed

The number and percentage of subjects with notable ECG values will be presented by treatment arm.

- QT parameter (QT, QTc) increase from baseline >30 ms, >60 ms
- Newly occurring post-baseline QT parameter > 450 ms, > 480 ms, > 500 ms
- HR increase from baseline $> 25\%$ and value > 100 bpm
- HR decrease from baseline $> 25\%$ and value < 50 bpm
- PR increase from baseline $> 25\%$ and value > 200 ms
- Newly occurring post-baseline PR > 200 ms and ≤ 220 ms, > 220 ms
- QRS increase from baseline $> 25\%$ and value > 110 ms
- Newly occurring post-baseline QRS > 110 ms and ≤ 120 ms, > 120 ms

The denominator to calculate percentages for each category is the number of patients with both a baseline and a post-baseline evaluation. A newly occurring post-baseline ECG notable value is defined as a post-baseline value that meets the criterion post-baseline but did not meet the criterion at baseline

- Frequency counts and percentages of patients with newly occurring post-baseline qualitative ECG abnormalities (morphology) will be summarized. The denominator to calculate percentages for any newly occurring ECG abnormality, each abnormality type and each individual finding is the number of patients with both a baseline and a post-baseline

evaluation, and baseline being normal, i.e. those patients who are at risk of developing this abnormality. A newly occurring post-baseline qualitative ECG abnormality is defined as a post-baseline abnormal finding which was not present at baseline

Patients with notable ECG interval values and newly occurring qualitative ECG abnormalities will be listed by treatment group, patient and timepoint, and the corresponding notable values and abnormality findings will be included in the listings.

Unscheduled ECG measurements will not be used in computing the descriptive statistics for change from baseline at each post-baseline time point. However, they will be used in the analysis of notable ECG changes and the analysis of notable QT parameters.

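### SAP 5.5.1 presumes triplicate ECGs that the protocol does not schedule, and its averaging rule conflicts with its own rule for abnormal and worst values, so the QTc threshold counts are not uniquely defined

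*SAP*

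**What the plan says.** **Number of ECGs.** SAP 5.5.1, under ECGs, says "For all patients, three ECGs are targeted to be measured at the protocol-defined (nominal) time-points". Protocol 7.2.2.5.4 says "A standard 12-lead ECG will be performed in accordance with" Table 7-4. That table gives one 12-lead row per time point, for example "Post-dose 4 hours (ECG should be performed just prior to drawing PK sample if both are scheduled simultaneously", and mentions no replicates. SAP Table 4-1, which lists departures from the protocol analyses, has no entry on this.

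**Averaging.** SAP 5.5.1 continues that, with more than one measurement at a nominal time, "the average of all available measurements associated with the nominal time point will be used for the analyses". It does not say which analyses.

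**Abnormal and worst values.** The opening paragraph of SAP 5.5.1 covers abnormal-assessment and worst-value analyses, names ECGs among them, and says "all post-baseline values will be included (scheduled, unscheduled, repeat". SAP 2.8.3.1 leaves unscheduled ECGs out of the by-time-point change statistics and then adds: "However, they will be used in the analysis of notable ECG changes and the analysis of notable QT parameters".

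**Outputs affected.** SAP 2.8.3.1 plans a QT/QTc shift table from baseline to the worst post-baseline value, counts of increases above 30 and 60 ms, and "Newly occurring post-baseline QT parameter > 450 ms, > 480 ms, > 500 ms".

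**Denominator.** For these notable values, "The denominator to calculate percentages for each category is the number of patients with both a baseline and a post-baseline evaluation". For qualitative ECG abnormalities, the same section restricts the denominator to patients with a normal baseline, on the ground that only they are at risk.

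**The concern.** The triplicate statement has no visible basis in the protocol, and it appears to be the reason for the averaging rule. Averaging planned triplicates reduces measurement noise. With one scheduled ECG, a second reading at the same nominal time may instead be a check on an unusual first one, and averaging then treats the reading and its check as equals.

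The SAP also gives two instructions for the same data. One programmer could apply the QTc thresholds to time-point means, another to individual readings, and each could cite SAP 5.5.1. QT prolongation is an adverse event of special interest, the protocol reports concentration-dependent prolongation in adults, and Amendment 7 extended ECG collection to the whole treatment period. These tables should not depend on who programs them.

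The denominator is a separate inconsistency. A patient who already meets a criterion at baseline cannot become a new case, yet is counted in the percentage.

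**Working it through.** The plan gives no figure to reproduce here. The check is a comparison of texts plus simple arithmetic.

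**1. ECGs per time point.** SAP 5.5.1: three. Protocol 7.2.2.5.4 and Table 7-4: one. The SAP premise does not match the protocol.

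**2. Which rule governs threshold counts?**

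| Text | Points to |
|---|---|
| SAP 5.5.1, opening paragraph | every reading, repeats included |
| SAP 2.8.3.1, unscheduled ECGs | unscheduled readings count toward notable values |
| SAP 5.5.1, ECG paragraph | mean at each nominal time, scope unstated |
| SAP 5.5.1, laboratory paragraph | worst value, stated expressly; the ECG paragraph has no such statement |
| SAP 2.8.3.1, correlation analysis | specifies individual, non-averaged readings; the notable-value and shift-table items do not |

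The first two rows favour individual readings and the other three leave averaging open. Including a value does not by itself mean analysing it individually: SAP 5.5.2 includes unscheduled pre-dose ECGs by putting them into the baseline average.

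**3. When averaging changes the count.** Take a first reading x > 500 ms and one repeat r at the same nominal time. The mean (x + r)/2 is no longer above 500 when r ≤ 1000 − x. With assumed readings (the documents give none):

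| x (ms) | r (ms) | Mean (ms) | Above 500 on the mean? | Above 500 on individual readings? |
|---|---|---|---|---|
| 505 | 490 | 497.5 | no | yes |
| 510 | 480 | 495 | no | yes |
| 510 | 495 | 502.5 | yes | yes |
| 540 | 470 | 505 | yes | yes |

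Three conditions must hold together: the repeat shares the nominal time, it is at or below 1000 − x, and averaging comes before the threshold. On individual readings the loss is zero.

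**4. How often could a repeat share the nominal time?** Protocol 7.2.2.5.4 requires daily repeats after a QTc above 500 ms, so most fall on later days. Table 6-4 allows an immediate repeat after a quality check, and a follow-up ECG within 24 hours or sooner. Same-time repeats are therefore possible, but their frequency is not documented.

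**5. Base rate.** Protocol 6.4.2.8 reports that 1 of 304 adults had a QTc above 500 ms and 10 had an increase above 60 ms. If those rates applied to the 83 treated children (an assumption), the expected numbers are 83 × 1/304 = 0.27 and 83 × 10/304 = 2.7 patients.

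**6. Denominator.** Let n patients have baseline and post-baseline ECGs, b of them meet the criterion at baseline, and x be new cases. The SAP reports x/n; the at-risk percentage is x/(n − b). The SAP figure is therefore (1 − b/n) times the at-risk one. With assumed n = 83, b = 8 and x = 5, that is 5/83 = 6.0% against 5/75 = 6.7%. Exclusion criterion 2 bars QTcF above 480 ms, so b should be close to zero for QTcF above 480 and 500 ms. The effect is mainly on the 450 ms category, QTcB, uncorrected QT, PR and QRS.

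**The case against.** The strongest reply is that the SAP already does what is needed. The opening paragraph of SAP 5.5.1 names ECGs and brings in all repeats for abnormal and worst values, and SAP 2.8.3.1 uses unscheduled ECGs for notable values. On that reading averaging affects only the by-time-point statistics and no case is missed. All ECGs are listed, so no reading is hidden, and events of special interest are identified from adverse event terms rather than averaged ECGs. This stands as a reason why an undercount is not established. It does not remove the conflict, because nothing in the ECG paragraph limits the averaging.

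A reader might go further and infer that the QTc counts will be biased low by a large, calculable amount. The documents do not support that. Any such size comes from the values chosen. Suppose normally distributed readings, a true QTcF of 480 to 490 ms and a within-patient SD of 10 to 20 ms. Given a first reading above 500, the mean with one repeat stays above 500 in only 6% to 54% of simulated cases. But the true value was set below 500, so averaging is mostly removing noise. With a true QTcF of 510 ms and SDs of 10, 15 and 20 ms, the mean stays above 500 in 97%, 93% and 90%. None of these inputs is in the documents.

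It can also be said that counting single worst readings is partly a preference, since Table 6-4 defines Grade 3 by at least two separate ECGs. That is fair, and a flag for confirmed values meets it. Finally, the SAP states its denominator openly. That makes it transparent, but it still departs from the at-risk rule that the same section uses for qualitative findings.

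**Conclusion.** Two defects in SAP 5.5.1 are established from the text: a triplicate premise that contradicts the protocol's single scheduled ECG, and an averaging rule without limits that conflicts with the same section's rule for abnormal and worst values. As written, the shift tables and the 450/480/500 ms and 30/60 ms counts can be programmed in two ways with different results.

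A lost QTc above 500 ms is possible under the averaging-first reading and impossible under the individual-reading one. The trial-level effect is unknown. It is probably small, because most repeats required after a high QTc fall on later days and, at the adult rate, fewer than one such patient would be expected among 83. With counts that low, though, one reclassified patient would be visible in the table.

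The denominator inconsistency is also real, with its effect mainly confined to the categories named in the last step of the working.

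**What to change.** 1. Correct the sentence on three ECGs in SAP 5.5.1 to match Table 7-4: one 12-lead ECG per scheduled time point.
2. State that averaging of multiple readings at a nominal time applies only to descriptive statistics by time point. The baseline average in SAP 5.5.2 is a separate rule and can stay.
3. State in SAP 5.5.1 and 2.8.3.1 that shift tables and all notable-value counts use individual centrally read post-baseline ECGs, including unscheduled and repeat readings. Optionally, flag values confirmed on a second ECG.
4. For each newly occurring QT, PR and QRS category, use as denominator the patients with baseline and post-baseline ECGs who did not meet that criterion at baseline.

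The cost is SAP wording and a programming rule, with no new data. The drawback is that isolated outlying readings will be counted; the optional flag lets a reader separate them from confirmed ones.

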5.5.2 Baseline

As defined in [Section 2.1.1](#), the last available assessment before or on the date of start of study drug is defined as “baseline” value or “baseline” assessment.

Laboratory data

If both central and local laboratory assessments were performed on the same date and corresponding to the baseline assessment date, then the central laboratory assessment will be used for the calculation of baseline.

ECGs

Baseline for ECG measurement is the average of all available measurements (unscheduled, if applicable) taken prior to dosing on the date associated with the last available ECG measurement before or on the date of start of study treatment. To determine whether ECG measurement was taken prior to dosing, ECG time will be compared with dosing time, if available. Unscheduled assessments will be included in the calculation of the average if ECG time is before dosing time. Study day one scheduled pre-dose ECGs will be considered to have been obtained prior to study drug administration if dosing time or ECG time is missing.

If a scheduled pre-dose measurement actually occurred post-dose, then the corresponding measurement will be treated and analyzed similar to an unscheduled post-dose measurement. For unscheduled assessments on study day 1,

- if dosing time is non-missing, then the assessment is classified as post-baseline if ECG time is later than dosing time.
- if dosing time is missing, the assessment is classified as post-baseline.

The same ECG assessments will be used for both qualitative and quantitative baseline evaluations.

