Baseline is the result of an investigation describing the “true” uninfluenced state of the patient. The last available assessment before or on the start date of study drug is defined as “baseline” value or “baseline” assessment, unless otherwise stated. If the assessment is planned to be performed prior to the first dose of study drug in the protocol and the assessment is performed on the same day as the first administration of study drug, it will be assumed that it was performed prior to study drug administration, if assessment time or first dose time is not collected or is missing. If assessment and first dose times are collected, the observed time point will be used to determine pre-dose on study day 1 for baseline calculation. Unscheduled assessments will be used in the determination of baseline. See [Section 5.5.2](#) for further details on derivation of baseline for laboratory data and ECGs.

Patients who start treatment and discontinue from the study on the same day may have two different sets of data collected on study day 1, one being reported to the cycle 1 day 1 visit, the other reported to the end of treatment (EOT) visit. Data reported at the EOT visit are not eligible for baseline selection.

Cohort

A group of newly enrolled patients treated at a specific dose and regimen (i.e. treatment group) at the same time. There may be more than one cohort at the same dose level.

Treatment group

Treatment group will generally be determined by the initially planned LDK378 dose level in mg/m² and regimen on Cycle 1 Day 1. For safety analysis, treatment group will be determined by dose and regimen received. Further details on the determination of treatment received is given in [Section 2.2](#). A treatment group can include several cohorts of patients who have received the same dose level and regimen but were recruited at the different point during the study. A treatment group may consist of one or more cohorts.

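### As worded, the SAP's ECG baseline rule returns no baseline for patients who follow the protocol's ECG schedule: it settles on Day 1, where every scheduled reading is post-dose, and has no fall-back to screening

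*SAP*

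**What the plan says.** **SAP 5.5.2, ECG paragraph.** Baseline is the average of the available readings "taken prior to dosing on the date associated with the last available ECG measurement before or on the date of start of study treatment". Pre-dose status is settled by clock time: "To determine whether ECG measurement was taken prior to dosing, ECG time will be compared with dosing time, if available". For missing times the section covers two kinds of Day 1 reading. One is the scheduled pre-dose ECG: "Study day one scheduled pre-dose ECGs will be considered to have been obtained prior to study drug administration" when either time is missing. The other is the unscheduled ECG, which counts as post-baseline if the dosing time is missing.

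**SAP 2.1.1.** The general definition begins "The last available assessment before or on the start date of study drug is defined as" baseline. It adds that, where assessment and dose times are both collected, the observed time decides what is pre-dose on Day 1. It then refers to 5.5.2 "for further details on derivation of baseline for laboratory data and ECGs".

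**Protocol Table 7-4.** There is one screening ECG, at any time from Day -28 to Day -1. The first Cycle 1 Day 1 entry reads "Post-dose 4 hours (ECG should be performed just prior to drawing PK sample if both are scheduled simultaneously"), and the second is the same at 6 h. There is no pre-dose entry for that day. The first scheduled pre-dose ECG on treatment is on Day 1 of Cycle 3.

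**SAP 2.8.3.1.** For notable ECG values, "The denominator to calculate percentages for each category is the number of patients with both a baseline and a post-baseline evaluation".

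**The concern.** The rule in 5.5.2 suits a trial with a scheduled pre-dose ECG on Day 1, and the current protocol has none. The last ECG date up to and including the start date is then Day 1 itself, and the pre-dose condition has nothing to select there.

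Several planned outputs need an ECG baseline: changes from baseline at each time point, the counts of QT or QTc increases above 30 ms and 60 ms, the QTc shift tables, and the newly occurring QTc, PR and QRS values. SAP 2.8.3.1 also uses baseline ECGs to judge whether the QT corrections are adequate and to estimate the slope for QTcP. A patient without a baseline drops out of all of these, including the denominators. QT prolongation is an adverse event of special interest for this drug, so the derivation should give one answer without a programmer having to choose.

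**Working it through.** The plan states no figure to reproduce. The check is to apply the rule to the schedule.

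**Inputs.** From Table 7-4: a screening ECG (placed at Day -7 for illustration, so 7 × 24 = 168 h before the first dose) and Day 1 ECGs at +4 h and +6 h. Write each reading as (study day, hours from first dose): (-7, -168), (1, +4), (1, +6).

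**Reading A, the word order of 5.5.2.** Date first: d* = the latest ECG day that is ≤ 1. Baseline = mean of readings with day = d* and hours < 0. Here d* = 1, and its readings are at +4 h and +6 h. Neither is below 0, so the set is empty.

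**Reading B, pre-dose filter first.** Keep readings with hours < 0, then take the last day among them. Only (-7, -168) survives, so d* = -7 and baseline is the screening ECG.

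**Reading C, date only, with no clock check.** Take the last reading with day ≤ 1. This is the one at +6 h.

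The same three readings for other patterns:

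| ECGs available | A: date first | B: pre-dose first | C: date only |
|---|---|---|---|
| Screening, Day 1 +4 h, Day 1 +6 h (Table 7-4) | none | screening | 6 h post-dose |
| Screening only | screening | screening | screening |
| Screening, unscheduled Day 1 pre-dose, +4 h, +6 h | Day 1 pre-dose | Day 1 pre-dose | 6 h post-dose |

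A and B differ only in the first row, and that row is the protocol schedule.

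**Is there a fall-back?** None of the sentences in the ECG paragraph of 5.5.2 says what to do when the selected date has no pre-dose reading. The missing-time provisions concern a scheduled Day 1 pre-dose ECG, which Table 7-4 lacks, and unscheduled Day 1 ECGs. They do not mention the scheduled 4 h and 6 h readings.

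**Reach.** The amendment log reports 40 + 20 = 60 patients by 22 September 2016 and 83 in total. Amendment 6 then removed the Day 1 post-dose ECGs for the expansion part, and Amendment 7 restored them. Most patients were therefore enrolled under a schedule with Day 1 post-dose ECGs. Both amendments required ethics approval before implementation and site dates are not given, so no exact count follows.

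**The case against.** The strongest reply is that the SAP, read as a whole, already leads to the screening ECG. Section 2.1.1 describes baseline as the patient's state before any drug influence and lets observed times decide what is pre-dose on Day 1. The opening of 5.5.2 points back to 2.1.1, and 2.1.1 refers to 5.5.2 only for further detail, which supplements its time check and does not cancel it. The assumption in 2.1.1 that an untimed Day 1 assessment was pre-dose covers only assessments planned before the first dose, so the nominal 4 h and 6 h readings never qualify. Empty baselines for most patients would also be noticed at first programming. Adverse events of special interest are identified by preferred term, and absolute QTc values by time point need no baseline, so those outputs are untouched.

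All of this stands, and it settles the intention. It also disposes of a stronger inference that a reader might draw, namely that the plan would use a post-dose reading as baseline and so subtract part of the drug effect. That needs reading C, which ignores both the pre-dose condition in 5.5.2 and the time check in 2.1.1. It is not a fair reading.

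What the reply does not do is supply the missing instruction. Section 5.5.2 is the specific rule for ECGs, its literal order gives an empty set on the protocol's own schedule, and no sentence sends the programmer to screening. Noticing the gap during programming would still leave the remedy to be chosen then.

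**Conclusion.** The point holds as a wording defect with real consequences if followed literally. For patients who follow Table 7-4, the ECG rule in 5.5.2 returns no baseline, although the SAP as a whole intends the screening ECG. Under the literal rule most patients would leave the baseline-dependent ECG summaries. Under the pre-dose-first reading none would.

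This assumes that patients had the scheduled Day 1 post-dose ECGs and no unscheduled pre-dose ECG that day. It also assumes that superseded versions of the ECG schedule, which are not available, had no Day 1 pre-dose ECG. Patients with no Day 1 ECG, or with an unscheduled pre-dose one, get a valid baseline under either order.

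Two further inferences go beyond the documents. A reader might subtract the enrolment counts in the amendment log to get an exact number affected, but those counts are not tied to implementation dates. A reader might also try to size a QTc bias from the accumulation ratio in Protocol 1.2.1.2.4. That would apply only to the excluded post-dose reading, and the ratio is an adult AUC figure at 750 mg, which says nothing direct about concentrations 4 to 6 h after a first paediatric dose.

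**What to change.** Replace the first sentence of the ECG paragraph in SAP 5.5.2 with wording to this effect:

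*Baseline ECG is the mean of all readings taken before the first dose on the last calendar date that has at least one such reading. If Day 1 has no pre-dose reading, this is the screening ECG. The nominal Cycle 1 Day 1 4 h and 6 h ECGs are always post-baseline, whether or not times are recorded.*

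The sentence on scheduled Day 1 pre-dose ECGs may stay. It has no effect under the current schedule and could matter if a superseded schedule included such a reading.

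The cost is one SAP paragraph and the matching line of the derivation program, with no new data. It should be made before database lock.
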